#### 11.4. Demographics

[figure not shown]
Demographics data include the subject's age, gender, and race/ethnicity. These data will be collected by site staff on a source document and entered into an eCRF.

#### 11.5. ECG

ECGs (12-lead resting) will be obtained in accordance with the schedule in [Table 6](#). Any abnormalities will be noted and an assessment of clinical significance will be done by a study physician. The ECG obtained at Day 1 prior to dosing will serve as the baseline for subsequent comparisons. When an ECG is scheduled at the same time as a blood collection, the ECG will be obtained prior to the blood collection. An appropriately qualified physician (preferably a cardiologist) at the study site (local reader) will read all ECGs. The local reader will write on the ECG tracing his/her global interpretation as either "normal ECG," "abnormal ECG - not clinically significant" or "abnormal ECG – clinically significant," then sign and date the ECG. In addition, the reader will complete the ECG worksheet. Only the local reader's reading of the ECG will be collected. The automatic machine reading will not be collected. Heart rate, RR

interval, and QT intervals will be reported on an eCRF. QTcF will be calculated using the Fridericia correction factor [ $QTcF = QT/RR^{(1/3)}$ ] ([Fridericia-1920](#)). The original ECG tracing will be retained in the subject's records at the study site.

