## **4.4. Mechanism of Action**

Kindolor was rationally designed to target systems that conduct sensory information from nociceptors and systems that transduce information between and within sensory neurons. At a

defined concentration range of  $<10 \mu\text{M}$ , kindolor significantly affects the function of multiple targets resident in peripheral sensory neurons. Kindolor does not engage a large number of other tested targets at concentrations  $\leq 10 \mu\text{M}$  and demonstrates an excellent therapeutic index based on pharmacologic and toxicologic studies in animals (estimated therapeutic index in rats  $\geq 18$ ). The targets identified through *in vitro* target binding and functional studies were the  $\text{Nav}1.7$  and  $\text{Nav}1.8$  VSNaCs, the NMDA receptor, the DOR, and the  $\text{GABA}_A$  receptor. There is ample evidence from the literature, that these receptors/ion channels are all contributors to development and maintenance of the peripheral sensitization component of chronic pain syndromes (Faber-2012, Ferrari-2014, Du-2017, François-2018, Hameed-2019, Xiao-2019, Quirion-2020, Lee-2012). Kindolor does not accumulate in brain and does not display CNS-mediated behavioral effects. An interesting observation regarding the NMDA and VSNaC receptors/ion channels that are targets for kindolor is that there is evidence that these targets are up-regulated in the course of development of chronic pain and the direction of kindolor's action (antagonist) would oppose the effects (hyperalgesia) generated by the up-regulation of the target NMDA and VSNaC receptors/ion channels.

Kindolor is an agonist at the DOR, which is another node in the chronic pain network. DORs are expressed along the length of sensory neurons and have been well demonstrated to localize in small diameter sensory neurons which also express  $\text{Nav}1.7$  and  $\text{Nav}1.8$ . DOR activation can reduce signal propagation from the peripheral receptors (François-2018; Bigliardi-2006; Quirion-2020, Gaveriaux-Ruff-2011; Gendron-2016).

In addition, kindolor also acts as a PAM at  $\text{GABA}_A$  receptors. Activation of the  $\text{GABA}_A$  receptors in the DRG has been demonstrated to abrogate painful sensory stimuli traversing nociceptors through the DRG (Du-2017).

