| Subject ID | Group | Visit | Visit Date | Test Name | Result | Units | Evaluation |
|------------|-------|-----------|------------|------------|--------|-------|---------------|
| xxxx | | Screening | mm/dd/yyyy | Hematocrit | | | WNL |
| | | Day 4 | | Hemoglobin | | | Abnormal, NCS |
| | | Week 4 | | RBC | | | Abnormal, CS |
| | | Week 8 | | WBC | | | |
| | | Week 12 | | Platelets | | | |
| | | | | xxxxxx | | | |

Listing 21: Coagulation

| Subject ID | Group | Visit | Visit Date | Test Name | Result | Units | Evaluation |
|------------|-------|-----------|------------|------------|--------|-------|---------------|
| xxxx | | Screening | mm/dd/yyyy | Fibrinogen | | | WNL |
| | | | | PT | | | Abnormal, NCS |
| | | | | PTT | | | Abnormal, CS |
| | | | | xxxx | | | |

Listing 22: Urine Drug Screen

| Subject ID | Group | Visit Date | Visit | AMP | Barb | Benzos | Coc | Opiates | Canab | Phen | Prop | Meth | Fen | Mor |
|------------|-------|------------|-------|-----|------|--------|-----|---------|-------|------|------|------|-----|-----|
| XXXX | | mm/dd/yyyy | | P | P | P | P | P | P | P | P | P | P | P |
| | | | | N | N | N | N | N | N | N | N | N | N | N |
| | | | | UNK | UNK | UNK | UNK | UNK | UNK | UNK | UNK | UNK | | |
| | | | | | | | | | | | | | | |
| | | | | | | | | | | | | | | |

P=positive; N=negative

AMP=amphetamine, , Barb=barbiturates Benzos=benzodiazepines, Coc=cocaine, Canab=cannabinoids, Phen=phencyclidine, Prop=propoxyphene, Fen=Fentanyl, Mor=Morphine

Listing 23: Vital Signs

| Subject ID | Group | Visit Date | Visit | Timepoint | Heart Rate (beats/min) | Systolic Pressure (mmHg) | Diastolic Pressure (mmHg) | Respiratory Rate (breaths/ min) | Temperature (°F) |
|------------|-------|------------|-------|-----------|---------------------------|--------------------------------|---------------------------------|--|---------------------|
| XXXX | | mm/dd/yyyy | | | xxx | xxx | xxx | | |
| | | | | | | | | | |
| | | | | | | | | | |
| | | | | | | | | | |
| | | | | | | | | | |

Listing 24: Electrocardiogram

| Subject ID | Group | Visit Date | Visit | Timepoint | Heart Rate (beats/min) | RR Interval (Sec) | QT Interval (msec) | QTcF (msec) | Interpretation |
|------------|-------|------------|-------|-----------|---------------------------|----------------------|--------------------------|----------------|----------------|
| xxxx | | mm/dd/yyyy | | | xxx | xxx | xxx | | |
| | | | | | | | | | |
| | | | | | | | | | |
| | | | | | | | | | |

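### PR and QRS are not planned numeric ECG variables, so a within-normal shift in conduction would not be summarised and a QRS change could not be told apart from a QT change

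*Protocol*

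**What the plan says.** Protocol section 11.5 defines what is kept from each ECG. On the source of the values it states "Only the local reader's reading of the ECG will be collected". It continues "The automatic machine reading will not be collected. Heart rate, RR" and completes that sentence with "interval, and QT intervals will be reported on an eCRF". QTcF is then calculated with the Fridericia formula. The local reader marks each tracing as normal, abnormal without clinical significance, or abnormal with clinical significance, and abnormalities are noted. Two further records exist: "In addition, the reader will complete the ECG worksheet", whose content is not described, and the paper trace, of which the protocol says "The original ECG tracing will be retained in the subject's records at the study site".

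The SAP follows this. After heart rate, the columns of Listing 24 are "RR Interval (Sec) | QT Interval (msec) | QTcF (msec) | Interpretation". SAP section 9.8 speaks of ECG parameters without listing them. Table 26 (numbered 36 in the SAP's list of tables) has one generic parameter row plus the three-level interpretation. Neither document names PR or QRS as a measurement.

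ECG results are a safety endpoint (Protocol 9.1, SAP 3.3), and Protocol 4.9 includes ECG in the data that the DSMB reviews before each escalation.

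**The concern.** Protocol section 4.4 names the sodium channels Nav1.7 and Nav1.8 among five targets. Of the sodium channels and the NMDA receptor it says that "the direction of kindolor's action (antagonist) would oppose the effects (hyperalgesia) generated by the up-regulation of the target NMDA and VSNaC receptors/ion channels". PR and QRS are the standard ECG measures of conduction. For a drug with sodium-channel antagonism in its described mechanism, given for the first time in humans over an 18-fold dose range (1800 mg / 100 mg), one would expect both to be tabulated.

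Two things are at stake. First, a graded, dose-related change in PR or QRS that stays within normal limits would leave no trace in the planned tables, because the interpretation category moves only when a reader calls the tracing abnormal. Second, QT runs from the start of QRS. A QRS change would therefore show as QTcF prolongation, and the planned variables could not say whether depolarisation or repolarisation had changed.

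**Working it through.** The documents give no figure of their own on this point, so the check has three parts.

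**1. Variables planned against variables needed**

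| Measure | Protocol 11.5 | SAP Listing 24 | SAP Table 26 |
|---|---|---|---|
| Heart rate, RR, QT | eCRF | yes | generic row |
| QTcF | calculated | yes | generic row |
| Three-level interpretation | yes | yes | yes |
| PR | not named | no | not named |
| QRS | not named | no | not named |

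The generic row in Table 26 can show only what the database holds. The machine reading, which might have supplied both intervals, is excluded.

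**2. How a QRS change enters QTcF**

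QT = QRS + JT. With JT and heart rate unchanged, the change in QT equals the change in QRS. The protocol's formula is QTcF = QT / RR^(1/3), so the change in QTcF is the change in QRS divided by RR^(1/3), with RR = 60 / heart rate in seconds. The QRS changes and heart rates below are assumptions, shown as a range.

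| Heart rate (bpm) | RR (s) | RR^(1/3) | QTcF change, QRS +5 ms | QRS +10 ms | QRS +20 ms |
|---|---|---|---|---|---|
| 50 | 1.200 | 1.063 | 4.7 | 9.4 | 18.8 |
| 60 | 1.000 | 1.000 | 5.0 | 10.0 | 20.0 |
| 75 | 0.800 | 0.928 | 5.4 | 10.8 | 21.5 |
| 90 | 0.667 | 0.874 | 5.7 | 11.4 | 22.9 |

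The multiplier runs from 0.94 to 1.14. With QRS recorded, JT = QT − QRS separates the two components. Without it, no planned variable does.

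**3. Tracings affected**

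- Scheduled per subject (Protocol section 5 and its schedule of assessments): screening, pre-dose, 2, 6, 12, 24 and 48 hours, follow-up = 8.
- All subjects: 8 × 32 = 256 at most.
- Active subjects: 6 × 4 = 24. Post-dose tracings at 2 to 48 hours: 24 × 5 = 120. With follow-up: 24 × 6 = 144.

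The 120 (or 144) is the number that bears on a drug effect; the rest are baseline or placebo tracings.

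**The case against.** The strongest case against is that nothing readable points to the heart. The named isoforms are Nav1.7 and Nav1.8, described as targets in peripheral sensory neurons. Section 4.4 adds that a large number of other tested targets are not engaged at 10 µM or below. Section 4.9 expects no cardiovascular effect at clinically relevant doses and reports no evidence of cardiovascular toxicity in vitro or in vivo. Section 4.7.1, on safety pharmacology, has no readable text, and hERG is in the abbreviation list but in no readable body text. Cardiac data may therefore exist that we cannot see. No hypothesis is tested (SAP section 6), and no ECG interval is a stopping criterion in Protocol 8.13.2.

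All of this stands, and it rules out a stronger reading. A reader might infer from the antagonist wording that kindolor is likely to slow cardiac conduction, or that the study is unsafe as planned. The documents support neither: they report no activity at a cardiac sodium channel, and the step from sensory-neuron isoforms to the heart would be the reader's own.

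A reader might also infer that conduction information is lost for good. That is too strong as well. A qualified physician reads every tracing, an overt abnormality would be noted, a large QRS change would at least move QTcF, and the retained tracings could be re-read. The worksheet might even hold the intervals.

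The narrower point survives. Animal and in-vitro results are what first-in-human ECGs are there to check. A possible re-read is not a planned analysis, and one prompted only by an abnormal call or a QTcF signal would not look for small within-normal shifts.

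**Conclusion.** The point holds as a gap in measurement. Followed as written, the plan gives a named safety endpoint no numeric measure of conduction, and leaves any QRS contribution to QTcF inseparable within the planned dataset. The size is near one-for-one transfer (multiplier 0.94 to 1.14 at 50 to 90 beats per minute) over 120 post-dose tracings on active drug, 144 with follow-up, out of up to 256 scheduled.

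This rests on three assumptions: JT and heart rate stay constant while QRS changes; the illustrative QRS changes of 5, 10 and 20 ms are not document figures; and the undescribed worksheet adds no intervals to the database. The documents give no ECG reading variability, so it cannot be shown that six active subjects per dose would resolve a small shift. The case is for recording and describing the values, not for a powered comparison. No dose, stopping rule or planned inference changes. I rate it a cheap improvement.

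**What to change.** In Protocol 11.5, add PR and QRS, as read by the local reader, to the ECG worksheet and to the values reported on the eCRF. In the SAP, name the ECG parameters in section 9.8 and add PR and QRS to Table 26 and Listing 24. Table 26 should give values and change from the Day 1 pre-dose ECG, which 11.5 already makes the baseline, by nominal time and dose with placebo pooled. The Table 26 shell repeats by visit, so it needs rows for the individual Day 1 times. JT is optional and needs no extra reading, since it is QT minus QRS.

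The cost is two eCRF fields, a few SAP rows, and slightly more reading and data-entry time on tracings already taken and already read by a physician. There is no new procedure, visit or burden on subjects. If subjects have already been dosed, the retained tracings can be read for the two intervals by a reader blinded to treatment; that costs up to 256 readings.

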### **11.6. Genetic Analysis**

### **11.7. Fecal Occult Blood Tests**

A FOBT will be performed to determine if any bleeding develops in the upper or lower GI tract. At the first screening visit, subjects will be provided with supplies and instructions on how to collect a stool sample and prepare a smear on a slide. The slide will be sent back to the clinical site laboratory for microscopic examination. A stamped and self-addressed mailer will be provided to the subject to return the specimen. If an FOBT is unable to be collected at intake day -1, the sample result from the closest bowel movement prior to subject dosing may be used.

### **11.8. Hepatitis and HIV Screen**

Hepatitis A virus immunoglobulin M (HAV-IgM), hepatitis B surface antigen (HBsAg), hepatitis C virus antibody (HCV Ab), and HIV antibodies (HIV Ab) tests will be performed at Screening. The laboratories performing these assessments should be directly regulated by the College of American Pathologists (CAP) or Clinical Laboratory Improvement Act (CLIA) guidelines.

### **11.9. Locator Form**

After signing informed consent, subjects will be asked to provide names, addresses, and phone numbers of several friends and/or family members who can be contacted if the subject cannot be located (Locator Form). This locator form will be used to assist in contacting subjects between visits and at follow-up. This form asks subjects his/her name, address, and phone number and to provide names, addresses, and phone numbers of several friends and family members who can be contacted if the subject cannot be located. This information is essential and will be collected during screening and will be updated throughout the study as necessary. This information will remain exclusively at the site.

### **11.10. Medical/Surgical History**

A complete medical history, including alcohol, tobacco and nicotine-containing and cannabis-containing product use histories will be taken at Screening for all potential study subjects to assure medical fitness. The medical history obtained at Screening will serve as the baseline for clinical assessment. Dates of prior surgeries will be recorded. The medical/surgical history will

be updated on Day -1 by asking the subject if anything has changed since the initial screening interview.

#### **11.11. Pregnancy Test and Birth Control Record**

An FDA-approved rapid result urine pregnancy test will be used (i.e., dipstick test). If applicable, subjects will be asked to sign a release of information form for study personnel to access medical records to obtain information regarding the outcome of a pregnancy that occurred during the study. The pregnancy test must be negative within the 72-hour period before clinic intake for the subject to be eligible for the study.

The Birth Control Assessment is designed to determine a female and male subject's compliance with the birth control specifications detailed in the inclusion criteria. Breast feeding status and sperm or ova donation status will be checked at screening, clinic intake, outpatient visits and final telephone contact.

#### **11.12. Prior and Concomitant Medications**

All medications taken by the subject 2 months prior to the start of screening, during the screening period, and through the final follow-up contact will be recorded on a source document and eCRF.

#### **11.13. Physical Examination, Height, and Weight**

A physical examination will be performed at Screening, and updated prior to dosing on Study Day 1, and prior to discharge from the site on Study Day 3 or upon premature termination. A symptom-directed physical examination will be performed, when necessary, at other times. Any significant physical examination findings after dosing will be recorded as an AE, if appropriate. Height will be measured only at Screening; the subject will not wear shoes. Body weight will be measured at Screening (for eligibility), prior to dosing on Study Day 1 (considered baseline weight for clinical assessment), at Day 7 or upon premature termination. The subject will wear lightweight clothing and no shoes during weighing. Height and weight will be recorded in cm and kg, respectively. BMI will be calculated as weight in kg divided by the square of height measured in meters.

#### **11.14. SARS-CoV-2 Test**

An FDA authorized SARS-CoV-2 antigen test will be performed within 72-hours before clinic intake and must be negative for the subject to be eligible for the study.

#### **11.15. Screen Failures Documentation**

To document the reason that a subject who consented to the study was not randomized, the Reasons the Subject Was Not Eligible eCRF will be completed for these subjects.

#### **11.16. Subject Disposition**

A subject disposition eCRF will be completed for all subjects who are randomized to the study and who are dispensed investigational product. This eCRF will be used to record the following

data as applicable: 1) completion status of the subject at the end of their participation and if they were discontinued early, and reason for early discontinuation.

### **11.17. Urine Drug Screen**

An FDA cleared, CLIA waived 14-panel urine drug test card will be used to assess candidates for recent use of amphetamines, barbiturates, benzodiazepines, buprenorphine, cocaine, fentanyl, MDMA, methadone, methamphetamine, morphine, opioids, oxycodone, phencyclidine, and THC. Recent alcohol use will be assessed using an FDA cleared, CLIA waived ethyl glucuronide urine test strip.

### **11.18. Vital Signs**

Vital signs to be assessed include sitting blood pressure, heart rate (after sitting for at least 3 minutes), oral temperature, respiration rate, and pulse oximetry in accordance with the schedule in [Table 6](#). Blood pressure, heart rate, respiration rate, and pulse oximetry will be measured prior to any blood draws.

### **11.19. Urine Output**

Urine output will be monitored over two 24-hour periods starting with the morning void on Day 1 and finishing through Day 3 prior to the morning void. The start time and end time of these two collection periods will be recorded and the amount collected during these 24-hour periods will also be recorded. As urine will also undergo other tests and some samples will be removed, the total volume during the collection period will be adjusted to account for any volumes removed for other tests. The timing of urine voids will also be recorded. Normal urine output is in the range of 800 – 2000 mL per 24-hour period. Urine output < 400 mL per 24 hours will be reported as an AE of oliguria. Urine output > 2500 mL per 24 hours will be reported as an AE of polyuria.

## **12. STATISTICAL METHODS AND DETERMINATION OF SAMPLE SIZE**

### **12.1. Statistical and Analytical Plans**

Complete details of the statistical analyses to be performed will be documented in a statistical analysis plan (SAP), which will be completed prior to locking and unblinding the study data. This document will include more detail of planned statistical analyses as well as table, listing, and figure shells. Any changes to the final SAP will be outlined in the final study report.

### **12.2. Analysis Populations**

The study analysis populations will consist of the following:

**Safety:** The safety population will include all subjects who received a dose of investigational product.

**PK:** The PK population will include subjects who received kindolor tosylate and had sufficient plasma concentrations to reliably calculate PK parameters.

### **12.3. Description of Statistical Methods**

#### **12.3.1. General Approach**

For descriptive purposes, dichotomous and categorical variables will be presented as number of observations and percentages; continuous variables will be given as means, standard deviations (SD), median, minimum (min), and maximum (max). All data will be presented in listings.

#### **12.3.2. Safety Analyses**

AEs will be coded using the most recent version of the MedDRA and will be grouped by system organ class (SOC) and preferred term (PT) designation. The severity, frequency, and relationship of AEs to investigational product will be presented by SOC and PT groupings by Cohort and Treatment. Placebo subjects from all cohorts will be considered the placebo group. Listings of each individual AE including start date, stop date, severity, relationship, outcome, and duration will be provided. Each AE (based on PT) will be counted once only for a given study subject. If the same AE occurred on multiple occasions, the highest severity will be assumed. Thus, study subjects are not counted multiple times in a given numerator in the calculation of frequencies for a specific AE.

GI AEs will also be summarized separately including stool consistency scores and presence/absence and severity of other symptoms according to the GI Signs and Symptoms checklist or endoscopy results if applicable. The GI AE scale scoring will be presented as summary statistics by categorical response. The presence, absence, and severity of other signs and symptoms of GI AEs indicative of possible gastric inflammation or erosion including endoscopy results will be presented as numbers and percentages, including if the GI AE triggered a study stopping criteria.

Clinical laboratory test results, urine drug screen results, and pregnancy test results will be reported as summary statistics for each assessment time point. Clinical chemistry, amylase,

lipase, hematology, coagulation, urinalysis, FOBT, urine drug screen results, and pregnancy test results will be presented as summary statistics and change from baseline. In addition, change from baseline (shift tables) will also be presented for clinical chemistry, amylase, lipase, hematology, and coagulation data. Vital signs and ECG parameters will be presented as summary statistics and change from baseline. The proportions of ECG results considered clinically significant will also be provided. Urine output in mL/hour will be calculated over the two 24-hour period of collection and presented as summary statistics for both periods. All data will be presented by treatment group.

